5.3.10.2 Adverse event collection and reporting

AE Collection

Upon enrolment into the trial, a subject's baseline conditions will be assessed (by documentation of medical history, concomitant diagnoses etc) at screening, and relevant changes from baseline will be subsequently noted.

Subjects will be required to report any AEs as well as the time of onset, end, and intensity of these events. In addition, each subject will be regularly assessed for AEs by the medical staff throughout the clinical trial and whenever the investigator deems necessary. As a minimum, subjects will be questioned for AEs (and concomitant therapies) at the time points indicated in [Flow Chart I](#) & [Flow Chart II](#). Where no AEs are observed at these time points, the Investigator, or other members of site staff should document, 'No AEs Observed'.

[figure not shown]
Assessment will be made using non-specific questions such as 'How do you feel?'. Specific questions will be asked wherever necessary in order to more precisely describe an AE.

The Investigator shall maintain and keep detailed records of all AEs in their patient files.

A careful written record of all AEs shall be kept by the investigator in charge of the trial. Records of AEs shall include data on the time of onset, end time, and intensity of the event as well as any treatment or action required for the event and its outcome.

The following must be collected and documented on the appropriate CRF(s) by the Investigator:

- From signing the informed consent onwards through the Residual Effect Period (REP), until individual subject's end of trial:
 - all AEs (serious and non-serious) and all AESIs.
 - The only exception to this rule are AEs (serious and non-serious) and AESIs in Phase I trials, when subjects discontinue from the trial due to screening failures prior to administration of any trial medication. In these cases, the subjects' data must be collected at trial site but will not be entered into the CRF or trial database and will not be reported in the CTR.
 - However, if an individual subject discontinues trial medication prematurely but stays in the trial (i.e. if further visits at home incl. telephone visits are planned) from then on and until the individual subject's end of the trial the Investigator must report related SAEs and related AESIs.
- After the individual subject's end of trial:
the Investigator does not need to actively monitor the subject for AEs but should only report relevant SAEs and relevant AESIs of which the Investigator may become aware of.

The REP for BI 433651 is defined as 30 days after the last trial medication application. All AEs which occurred through the treatment phase and throughout the REP will be considered as on treatment, please see [Section 7.3.4](#). Events which occurred after the REP and before trial termination date will be considered as follow-up events.

AE reporting to sponsor and timelines

The Investigator must report SAEs, AESIs, and non-serious AEs which are relevant for the reported SAE or AESI, on the BI SAE form via fax immediately (within 24 hours) to the sponsor's unique entry point (country specific contact details will be provided in the ISF). The same timeline applies if follow-up information becomes available. In specific occasions the Investigator could inform the sponsor upfront via telephone. This does not replace the requirement to complete and fax the BI SAE form.

With receipt of any further information to these events, a follow-up SAE form has to be provided. For follow-up information the same rules and timeline apply as for initial information.

Information required

For each AE, the Investigator should provide the information requested on the appropriate CRF pages and the BI SAE form. The Investigator should determine the causal relationship to the trial medication and any possible interactions between the investigational drug and a Non-Investigational Medicinal Product (NIMP).

The following should also be recorded as an (S)AE in the CRF and SAE form (if applicable):

- Worsening of the underlying disease or of other pre-existing conditions
- Changes in vital signs, ECG, physical examination and laboratory test results, if they are judged clinically relevant by the Investigator.

If such abnormalities already pre-exist prior trial inclusion they will be considered as baseline conditions.

All (S)AEs, including those persisting after individual subject's end of trial must be followed up until they have resolved, have been sufficiently characterised, or no further information can be obtained.

Pregnancy

In rare cases pregnancy may occur in a clinical trial. Once a subject has been enrolled into this clinical trial and has taken trial medication, the Investigator must report immediately (within 24 hours) any potential drug exposure during pregnancy (DEDP) to the sponsor's unique entry point (country-specific contact details will be provided in the ISF). The Pregnancy Monitoring Form for Clinical Trials (Part A) should be used. This includes if the subject is female and becomes pregnant, or the subject is male and his female partner becomes pregnant.

The outcome of the pregnancy associated with the drug exposure during pregnancy must be followed up and reported to the sponsor's unique entry point on the Pregnancy Monitoring Form for Clinical Trials (Part B).

The ISF will contain the Pregnancy Monitoring Form for Clinical Trials (Part A and B).

As pregnancy itself is not to be reported as an AE, in the absence of an accompanying SAE and/or AESI, only the Pregnancy Monitoring Form for Clinical Trials and not the SAE form is to be completed. If there is an SAE and/or AESI associated with the pregnancy an SAE form must be completed in addition.

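### Protocol 5.3.10.2 contradicts itself on AE collection after an early stop of trial medication; on a natural reading, non-serious on-treatment AEs of CF subjects could stay off the CRF.

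*Protocol*

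**What the plan says.** Protocol 5.3.10.2 lists what must go on the CRF. From informed consent through the REP to the individual's end of trial, that is "all AEs (serious and non-serious) and all AESIs". Screening failure before any dose is then carved out: "The only exception to this rule are AEs (serious and non-serious) and AESIs in Phase I trials".

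The next sub-bullet opens with the word However. Its trigger is "if an individual subject discontinues trial medication prematurely but stays in the trial (i.e. if further visits at home incl. telephone visits are planned" (the bracket closes there). From that point until the subject's "end of the trial the Investigator must report related SAEs and related AESIs". For the time after the end of trial, a separate bullet says that the investigator "should only report relevant SAEs and relevant AESIs of which the Investigator may become aware of".

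The same section also says:
- On analysis status: "All AEs which occurred through the treatment phase and throughout the REP will be considered as on treatment". The REP is 30 days after the last application.
- On information required: CRF details are asked for each AE, with no limit by seriousness, relatedness or treatment status.
- On reporting to the sponsor: "The Investigator must report SAEs, AESIs, and non-serious AEs which are relevant for the reported SAE or AESI". SAEs carry no relatedness limit here.
- On source records: "The Investigator shall maintain and keep detailed records of all AEs in their patient files".

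Flow Chart II footnote 16 has AEs recorded for the whole trial. Section 6.2.2 has them assessed continuously up to the end-of-trial examination. Section 6.2.3 sends early stoppers through follow-up and the end-of-trial visit.

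On the analysis side, Protocol 7.3.4 and SAP 6.1 (Table 6.1: 2) assign AEs to the preceding treatment up to the end of the REP, unless the next period's first dose or trial termination comes first. SAP 7.8.1 works from eCRF data. SAP 7 bases percentages on all subjects in the analysis set.

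**The concern.** The section names a sole exception and then follows it with what looks like a second one. If a site applies the sub-bullet as a reduction, it stops entering non-serious AEs, and unrelated events generally, once a subject stops medication. The analysis still counts the following 30 days as on treatment.

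The primary endpoint is the percentage of subjects with any TEAE. An AE that is not on the eCRF cannot be told apart from no AE, and the subject stays in the denominator. SAP 6.6 imputes no missing safety data apart from incomplete AE dates, and the SAP has no flag for reduced collection after a stop. Any error would make the treatment with more early stops look better tolerated than it was.

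The point is confined to Part 2. The trigger's bracket refers to home and telephone visits, which fits CF subjects (Flow Chart II has a telephone call on Day 23). Healthy volunteers are followed up in the clinic, so it is doubtful that the clause reaches them.

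**Working it through.** The plan gives no figure on this point to reproduce. The check sets the texts side by side and then works out the size.

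**1. Which texts conflict with the narrow reading**

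| Text | Required after an early stop | Fits a reduction? |
|---|---|---|
| 5.3.10.2, parent bullet | All AEs and AESIs to end of trial | No |
| 5.3.10.2, sole exception | Screening failures only | No |
| 5.3.10.2, information required | CRF details for each AE | No |
| Flow Chart II footnote 16; 6.2.2 | AEs for the whole trial | No |
| 5.3.10.2, However sub-bullet | Related SAEs and related AESIs | Source of the conflict |

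The REP statement in 5.3.10.2, Protocol 7.3.4 and SAP 6.1 are assignment rules. They do not say what is collected; they show what a gap would do to the endpoint.

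**2. Weight of one subject**

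Inputs: 24 CF subjects planned, each to receive both treatments (Protocol 3.1); at least 20 to complete both periods (3.3.5).

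Shift per subject whose only TEAE is not entered = 100 / N.
- N = 24: 100/24 = 4.2 points.
- N = 20: 100/20 = 5.0 points.
- A stopper already counted with a TEAE on that treatment: 0 points.

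**3. Expected shift for one stopper with no earlier TEAE**

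The documents give no AE rate, so assume a chance p of 0.1 to 0.5 of a first AE in the 30 days after the stop. Expected shift = 100 × p / 24:
- p = 0.1: 0.4 points.
- p = 0.3: 1.25 points.
- p = 0.5: 2.1 points.

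These assume that every such AE is of a kind the sub-bullet omits and goes unentered.

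**4. Share of the window affected**

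On-treatment window = day of last dose + 30.
- Last dose on Day 7: 7 + 30 = 37 days, of which 30 (30/37 = 81%) fall under the narrow text and 7 (19%) under the full rule.
- Completer, nominal: 14 + 30 = 44 days, all under the full rule. With the Day 14 visit up to 3 days late, 17 + 30 = 47.

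Windows are shorter if period 2 dosing or trial termination comes first.

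**The case against.** **The sub-bullet need not reduce anything.** It says what must be reported and has no limiting word, while the bullet on the time after end of trial does say only. It could set a floor for subjects with reduced contact, or concern transmission to the sponsor. This stands as far as it goes: a reader might infer that the protocol definitely restricts collection, and the wording does not establish that. But the clause sits under the CRF list and opens with However, and sponsor reporting has its own paragraph. The reduction remains a natural reading, and sites may differ.

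**Few subjects could be affected.** This stands. A shift needs a subject who stops early, stays in the trial, has had no TEAE on that treatment, and then has a first non-serious AE within 30 days. Many stop reasons in Protocol 3.3.4 are AEs or would normally be recorded as such, so those subjects are already counted. A reader might take the margin from 24 subjects to 20 completers and infer a shift of 16.7 points (4/24). That would need four stoppers on one treatment, all TEAE-free at the stop and all with a later unentered event. Section 3.3.5 also counts people who leave the trial or fall outside the compliance range as non-completers, so the margin does not measure early stoppers who remain.

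**There are safeguards.** Also true. Subjects are questioned about AEs at the flow-chart times, patient files must hold all AEs, discrepancies between CRF and source must be explained (8.3.1), and CRF accuracy is verified against source (8.3.2). These make silent loss less likely. They do not settle which rule a monitor should verify against.

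**Conclusion.** The contradiction is in the current protocol text. Most of the plan favours full capture, and one sub-bullet is out of line with it. If a site follows the narrow reading, each CF early stopper whose only TEAE is a non-serious event after the stop lowers that treatment's any-TEAE rate by 4.2 points (5.0 with 20 subjects). The number affected is probably 0 to 1; this is a judgement from the stop reasons and the source checks, not a figure in the documents. Later non-serious events of other stoppers could still be missing from the preferred-term and intensity tables.

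Two stronger inferences are not supported. A reader might conclude that AEs have been lost; nothing in the documents shows this, and the patient files allow recovery. A reader might also conclude that unrelated SAEs would go unreported; the sponsor-reporting paragraph asks for SAEs without a relatedness limit, so that is less likely.

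The analysis is descriptive, with no hypothesis test at risk. Severity: minor to should-fix.

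**What to change.** Delete the sub-bullet. State in its place that all AEs, SAEs and AESIs are entered on the CRF for every treated subject through the REP and until that subject's end of trial, whether or not trial medication was stopped.

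Before database lock, check the patient files of early stoppers for AEs that were not entered, and enter them. Flag a subject in the outputs only if AE follow-up is found to be incomplete. Keep all treated subjects in the main TEAE table.

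The cost is one protocol sentence, a file check for a handful of subjects at most, and a few more AE records. No visits are added, because section 6.2.3 already keeps early stoppers in follow-up.

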| | 312:00 | 08:05 | |
| | | 08:15 | |
| | 312:15 | 08:30 | |
| | | 08:45 | |
| | 313:00 | 09:00 | |
| | | 10:00 | 250 mL water intake, thereafter, breakfast ¹² allow home |
| | 528:00 | 00:00 | telephone call |
| | | 08:00 | |
| | 696:00 | 00:00 | in-clinic visit |
| | | 08:00 | |
| | | | Safety Laboratory ³ |
| | | | PK _{blood} |
| | | | 12-lead ECG ⁶ |
| | | | CASA-Q & CFQ-R |
| | | | |
| | | | Pulmonary function testing ⁵ |
| | | | Vital signs (BP, PR) ¹⁸ |
| | | | Adverse events / Concomitant Meds ¹⁶ |

After Day 14 of Visit 2 (Period 1), subjects will washout for at least 30 days prior to crossing-over and commencing Day 1 of Visit 3 (Period 2). A second baseline (Day-7 to -3) will be conducted within the washout period. At the end of Visit 3 (Period 2), subjects will continue to the end of study visit (Visit 4).

| | | After Day 14 of Visit 2 (Period 1), subjects will washout for at least 30 days prior to crossing-over and commencing Day 1 of Visit 3 (Period 2). A second baseline (Day-7 to -3) will be conducted within the washout period. At the end of Visit 3 (Period 2), subjects will continue to the end of study visit (Visit 4). | | | | | | | | | | | |
|--------|-------|--|--|--|---|---------------------------------------|--------------------------------|---------------------|--------------------------|----------------|---|------------------------------------|---|
| Period | Visit | Day | Planned Time relative to first drug administration [h:min] | Planned Time relative to first drug administration [h:min] | Approximate clock time (actual day) [h:min] | Event and comment | Safety Laboratory ³ | PK _{blood} | 12-lead ECG ⁶ | CASA-Q & CFQ-R | Pulmonary function testing ⁵ | Vital signs (BP, PR) ¹⁸ | Adverse events / Concomitant Meds ¹⁶ |
| EOS | 4 | -44-51 | 9999:00 | 00:00 | 08:00 | e.o.s. ⁹ , in-clinic visit | X ¹⁹ | x | x | | x | x | |

Note: The cumulative times specified in the planned time column are for orientation only. Depending on the actual a.m. dosing time at the given day, the procedures and observations related to that a.m. dosing (such as pre a.m. dose and post a.m. dose measurements of the same day) have to be adapted respectively:

Proprietary confidential information © 2017 Boehringer Ingelheim International GmbH or one or more of its affiliated companies

- Pre-dose procedures will be performed in the following order, ensuring that PK bloods take priority with regards to timing:
 1. ECGs
 2. Vital signs
 4. PFTs

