 5. Safety labs/ PK blood (on the time-point)
 6. Meals
- Post-dose procedures will be performed in the following order, ensuring that PK bloods take priority with regards to timing:
 1. ECGs
 2. Vital signs
 4. Safety labs/ PK blood (on the time-point)
 5. PFTs
 6. Meals

- If mentioned at the same time point meals will be served after completion of the planned procedure (i.e. PK, pulmonary function).
- Urinalysis and urine samples can be performed any time pre-dose.

- 1) Screening including subject information, informed consent, physical examination and review of vital signs/ECG/safety laboratory tests, drug screening; additionally, demographics including determination of the body weight/height, smoking and alcohol history, relevant medical history, concomitant medication, pregnancy test for female subjects and review of inclusion/exclusion criteria.
- 2) Pre-dose blood samples for PK will be taken from approximately 15 minutes prior to dosing. All remaining PK samples will be taken as close as possible to the planned times, as mentioned in [section 6.1](#).
- 3) Full Clinical Safety Labs as per [section 5.3.7](#), unless otherwise specified. Safety labs for electrolytes should be centrifuged and stored as per requirements in section 5.3.7.
- 4) Must be completed and medically evaluated within 7 days prior to administration of study drug; this safety laboratory can be omitted, if the screening examination is performed on Days -7, -6, -5, -4 or -3. Female subjects of childbearing potential will have progesterone levels measured (between Day 7 and Day 10 of their pill packet) during the screening period and Day -5 to -3 then prior to the second treatment period.
- 5) Should be completed at relevant visits. Pulmonary function to be performed using Investigative site spirometry equipment (FEV₁, FVC, FEF₂₅₋₇₅) at in-house visits except Day -7 to -3 of each treatment period. (FEV₁) to be used at home (ex-clinic).
- 6) ECGs will be recorded for a 10-sec duration after the subjects have rested for at least 5 min in a supine position
- 7) All pre-dose measurements should be completed prior dosing. Dosing will be under supervision at the trial site during all in-house test-days (Period 1 & 2 - Days 1, 7, and 14).
- 9) End-of-study visit; including physical examination, review of vital signs/ECG/laboratory at the end-of-study examination
- 12) If several actions are indicated at the same time point, the intake of fluids/meals will be the last action.

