* Subjects receiving placebo are equally distributed across dose groups

Table 4.1.4: 2

Treatment overview CF

| Treatment | Formulation, dose regimen | Route of administration | Number of actuations per single administration | Unit strength [µg] | Total dose per Administration [µg] | Posology distribution over the treatment period |
|-----------|---|-------------------------|--|--------------------|------------------------------------|---|
| 1 | Inhalation solution, 27 administrations ** 12 hours apart | Inhalation | 2 | 300 | 600 | Day 1 to Day 13 a.m./ p.m. and Day 14 a.m. |
| Placebo* | Inhalation solution, 27 administrations 12 hours apart | Inhalation | Matching active treatment | - | - | Day 1 to Day 13 a.m./ p.m. and Day 14 a.m. |

* Each subject will receive active and placebo

** Theoretical number of administrations when no time windows applied

Each newly assembled RESPIMAT Inhaler has to be primed by qualified, trained, unblinded study personnel, e.g. pharmacist at the trial site under the responsibility of the investigator, who is not involved in the conduct of the trial. Except those devices used for training, priming should NOT take place in the same room where the subject is inhaling trial medication or PK sample preparation. The inhaler should be primed by actuating it until an aerosol is visible plus three additional actuations. For detailed priming instructions please refer to the RESPIMAT Inhaler handling instructions in [Appendix 10.1](#).

Both the study drug as well as the placebo treatment (depending on randomisation) will be inhaled with the RESPIMAT in a sitting or standing position under supervision of the investigating physician or an authorised designee (see [section 4.3](#)). Inhalation of study drug should NOT take place in the same room where the blood samples are taken, to prevent contamination of samples from airborne drug. If more than one actuation is needed, planned time 0:00h will always be the first actuation. If more than one actuation will be needed, the duration from first to last actuation will be recorded. After study drug inhalation, subjects will drink 250 mL of water.

The so-called four-eye principle (two-person rule) should be applied for administration of trial medication and – if applicable – its preparation (e.g. assembling of device), if correct dosage cannot be ensured otherwise.

For restrictions with regard to diet see [section 4.2.2.3](#).

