6.2.2 Treatment period(s)

Each subject will receive the respective trial medication (BI 443651 or placebo b.i.d.) at Day 1 until Day 6 for healthy volunteers, and Day 13 for CF subjects, and then one dose of the respective trial medication (BI 443651 or placebo) in the morning of the final day. CF subjects will undergo subsequent washout period of at least 30 days prior to an additional two weeks of respective trial medication i.e. the alternative medication administered during the first treatment period.

Trial medication will be administered by each subject (under direct supervision, whilst in-clinic of the investigator or his designee). Details on treatments and procedures of administration are described in [Section 4.1.4](#).

All healthy volunteers and CF subjects will attend the trial site, as per [Flow Chart I & Flow Chart II](#), after formal assessment and confirmation of their fitness by the investigator or designee. On all other study days, the study will be performed in an ambulatory fashion (at home / ex-clinic).

For details on time points and procedures for collection of plasma samples for PK analysis, refer to [Flow Chart I & Flow Chart II](#).

The safety measurements performed during the treatment period are specified in [Section 5.2](#) of this protocol and in [Flow Chart I & Flow Chart II](#). For details on time points for all other trial procedures, refer to [Flow Chart I & Flow Chart II](#). AEs and concomitant therapy will be assessed continuously from screening until the end of trial examination.

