7.3.4 Safety analyses

Safety will be assessed for the endpoints and parameters of interest listed in [Section 5.1.1](#) and [5.1.3](#) based on the treated set. Safety analyses (except of ECG data) will be descriptive in nature and will be based on BI standards.

Treatments will be compared in a descriptive way. The control group for HV in the safety evaluation will consist of all placebo treated subjects, regardless of the dose group in which they were treated. For CF, each subject will appear in the active treatment group and the placebo group, due to the cross-over structure. The active treatment groups will be compared to the respective placebo group in a descriptive way. Tabulations of frequencies/proportions will be used for the evaluation of categorical (qualitative) data, and tabulations of descriptive statistics will be used to analyse continuous (quantitative) data.

The analyses will be done by 'randomised treatment'.

Measurements (such as ECG, vital signs, or laboratory parameters) or AEs will be assigned to treatments ([see Section 4.1](#)) based on the actual treatment at the planned time of the measurement or on the recorded time of AE onset (concept of treatment emergent AEs).

Therefore, measurements planned or AEs recorded prior to first intake of trial medication will be assigned to 'screening', those between first trial medication intake until next intake or the end of REP will be assigned to the preceding treatment, and all AEs occurring between the end of REP and next treatment intake or trial termination date respectively will be assigned to 'follow-up'. In case of two or more treatments, the follow-up will be summarized according to the previous treatment. These assignments including the corresponding time intervals will be defined in detail in the TSAP. Please note that AEs occurring after the last per protocol contact but entered before database lock will be reported to drug safety only and will not be captured in the trial database.

Adverse events that start before first drug intake and deteriorate under treatment will also be considered as 'treatment emergent'.

Additionally, further treatment intervals (analysing treatments) may be defined in order to provide summary statistics for time intervals, such as combined treatments, on-treatment totals or periods without treatment effects (such as screening and follow-up intervals).

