10.7 CONTRACEPTION SECTION

All female subjects (and female partners of male subjects) are regarded as being of childbearing potential unless they are either post-menopausal or permanently sterilised. Post-menopausal is defined as having had, at least, 12 months spontaneous amenorrhea with an appropriate clinical profile (age, vasomotor symptoms, etc.). Females may have

been permanently sterilised by means of hysterectomy, bilateral salpingectomy, bilateral oophorectomy, confirmed tubal occlusion or tubal ligation.

All female subjects of child bearing potential must use two acceptable methods of contraception with their partners, from screening until 30 days after the last dose of IMP. Male subjects with female partners of child bearing potential must use condoms plus any one other acceptable method of contraception together with their partners, from first dose until 3 months after the last dose of IMP. Alternatively, true heterosexual abstinence is also acceptable (this must be due to subject's lifestyle choice i.e. the subject should not become abstinent just for the purpose of study participation; withdrawal or calendar methods are not considered acceptable).

Acceptable methods of contraception for female subjects:

[figure not shown]
[figure not shown]
[figure not shown]
[figure not shown]
[figure not shown]
- Condoms
- Established hormonal contraception in the form of combined oral monophasic contraception

[figure not shown]
Proprietary confidential information © 2017 Boehringer Ingelheim International GmbH or one or more of its affiliated companies

Acceptable methods of contraception for male subjects with female partners of childbearing potential include:

- Condoms
- Established hormonal contraception
- Intrauterine device (IUD) / intrauterine hormone-releasing system (IUS).

Male subjects with pregnant partners are excluded. Male subjects must not donate sperm until 3 months after the dose of IMP

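### Flow Chart II allows a compliant Period 2 end-of-study visit in CF subjects 1 to 3 days before the 30-day residual effect period ends

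*Protocol*

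**What the plan says.** **AE collection.** Protocol 5.3.10.2: "The REP for BI 433651 is defined as 30 days after the last trial medication application" (the compound number is transposed there; the study drug is meant). The same section asks for all AEs from consent through the REP until the subject's own end of trial, and counts events in the REP as on treatment. After the subject's end of trial there is no active monitoring; the investigator reports only relevant SAEs and AEs of special interest that come to notice. Section 7.3.4 adds that "AEs occurring after the last per protocol contact but entered before database lock will be reported to drug safety only" and are not held in the trial database.

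**Last CF dose.** Section 6.2.2 has twice-daily dosing to Day 13, "then one dose of the respective trial medication (BI 443651 or placebo) in the morning of the final day". Flow Chart II, footnote 7, ties that dose to the visit: "Dosing will be under supervision at the trial site during all in-house test-days (Period 1 & 2 - Days 1, 7, and 14". Flow Chart II gives the Day 14 visit a window of -1/+3 days. A footnote to Table 4.1.4: 2 qualifies the count of 27 doses: "Theoretical number of administrations when no time windows applied".

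**End of study.** Flow Chart II places Visit 4 at Day 44-51, and SAP Table 6.7: 2 repeats the range. It follows the second period directly: "At the end of Visit 3 (Period 2), subjects will continue to the end of study visit (Visit 4").

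**Analysis phase.** SAP Table 6.1: 2 closes the CF on-treatment phase at the end of the REP, at trial termination or at the first dose of the next period, whichever is earliest.

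**The concern.** The end-of-study range is fixed in study days, while the REP runs from the actual last dose. Once the last dose is allowed to move and the visit is not, the two agree only if the last dose is on Day 14 or earlier. A site can then follow the flow chart and close a subject's AE collection before the period that 5.3.10.2 says must be covered. The primary endpoint is the frequency of subjects with treatment-emergent AEs, and REP events count towards it. A non-serious AE in the uncovered days would not reach the database, and no protocol deviation would be recorded, because the visit was on schedule.

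Period 1 is not exposed in the same way. Flow Chart II describes the washout of at least 30 days as lying between drug administrations, and AEs continue to be asked about when the subject returns for Period 2. Only Period 2 ends with a last contact.

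**Working it through.** **Inputs**
- REP: 30 days after the last dose (Protocol 5.3.10.2).
- Permitted last-dose days: 13 to 17 (Flow Chart II, Day 14 at -1/+3 days).
- Permitted end-of-study days: 44 to 51, which is 8 days (Flow Chart II; SAP Table 6.7: 2).
- Convention: a visit on the last day of the REP covers it.

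**Step 1: reproduce the plan's own figure.** End of REP = last-dose day + 30.
- CF, nominal: 14 + 30 = 44. In planned hours, Day 14 is 312 h; 312 + 30 × 24 = 1032 h; 1032 / 24 + 1 = Day 44. This is the day the window opens.
- Healthy volunteers: 7 + 30 = 37, which is where their Day 37-44 window opens (Flow Chart I).

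In both parts the visit opens exactly when the REP ends after the nominal last dose.

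**Step 2: move the last dose through its window.** Shortfall = max(0, last-dose day + 30 − end-of-study day).

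| Last dose | REP ends | Days from last dose to a Day 44 visit | Shortfall at Day 44 | Permitted visit days that fall short |
|---|---|---|---|---|
| Day 13 | Day 43 | 31 | 0 | none |
| Day 14 | Day 44 | 30 | 0 | none |
| Day 15 | Day 45 | 29 | 1 | 44 |
| Day 16 | Day 46 | 28 | 2 | 44, 45 |
| Day 17 | Day 47 | 27 | 3 | 44, 45, 46 |

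Of the 5 × 8 = 40 permitted pairings of last-dose day and visit day, 0 + 0 + 1 + 2 + 3 = 6 fall short. This counts what is allowed; it does not estimate how often it happens, which the documents do not show.

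**Step 3: scale it.** Under SAP 6.1 the on-treatment phase runs from the first dose of the period to the end of the REP. For a Day 17 last dose that is about 47 days, so the worst case loses 3 / 47 = 6.4% of it. As a share of the REP alone it is 3 / 30 = 10%.

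**Step 4: look for a rule that closes the gap.**
- The note to Flow Chart II on adapting planned times covers procedures around that day's morning dose. It does not move Visit 4.
- The earliest-of rule in SAP Table 6.1: 2 assigns whatever was collected. It does not lengthen collection.
- Days 47 to 51 cover every permitted last dose, so the existing window could be used safely, but nothing tells the site to do so.

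**The case against.** The strongest reply is that 5.3.10.2 already requires collection through the REP, and that a site can meet both that rule and the flow chart by choosing Day 47 or later. Collection stops early only if the subject's end of trial means Visit 4, and the protocol does not define that term. This is fair as far as it goes. But 6.2.2 has AEs assessed until the end-of-trial examination, and 7.3.4 cuts off at the last per-protocol contact. Both favour reading it as Visit 4. A flow chart that permits a date the text rules out still needs correcting.

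Three further objections stand, and they limit the point:
- **Share of the primary endpoint.** A reader might infer that a tenth of the endpoint's window is lost. The window starts at the first dose, not at the last. A subject last dosed on Day 17 and seen on Day 44 is observed over Days 1 to 44, the same span as a subject on the nominal schedule. Only the tail after the last dose is shorter.
- **Bias between treatments.** A reader might infer that the comparison with placebo is distorted. Sequences are allocated 1:1, so Period 2 contains both treatments, and nothing in the documents suggests that the windows are used differently by treatment.
- **Contraception and pregnancy testing.** A reader might infer a breach here. The duty for women runs "from screening until 30 days after the last dose of IMP" whatever the visit date, and pregnancies are reported separately under 5.3.10.2. No section requires the final pregnancy test, laboratory tests or ECG to fall at or after the end of the REP.

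**Conclusion.** The conflict is real and small. A compliant end-of-study visit in Period 2 can fall 1, 2 or 3 days before the REP ends, at the extreme 27 days after the last dose, although 5.3.10.2 asks for all AEs through 30 days. Non-serious AEs in the missing days would not be captured in the trial database.

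It rests on two readings: that the last dose is taken at the moved Day 14 visit, which footnote 7 and the footnote to Table 4.1.4: 2 support, and that a subject's end of trial is Visit 4, which is inferred. It needs both a last dose on Day 15-17 and a visit in the first one to three days of its window. With at most 3 of about 47 on-treatment days affected, under either treatment, the effect on the percentage of subjects with a treatment-emergent AE is probably slight. The documents do not support a claim that the primary result would be materially altered.

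It looks like an oversight rather than a choice. Both parts open the visit exactly 30 days after the nominal last dose. The amendment history lists the Day 14 window among the version 8 changes, with no matching change to the CF end-of-study range.

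**What to change.** In Flow Chart II, define the CF end-of-study visit as 30 to 37 days after the actual last dose of Period 2. For a Day 14 last dose this is 44 to 51, as now; for Day 17 it is 47 to 54. The shortfall is then zero for every permitted last-dose day. A smaller edit with the same effect on the shortfall is to keep Day 44-51 and add that the visit may not be earlier than 30 days after the last dose; Days 47 to 51 already allow this in the worst case.

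Align the day label in SAP Table 6.7: 2 for consistency only. That table is the ECG schedule and does not govern AE collection. The AE phases in SAP 6.1 and Table 6.1: 2 already count the REP from the last dose and need no change. It would also help to state in 5.3.10.2 that a subject's end of trial is Visit 4.

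The cost is one flow-chart line and one table label. A few visits move later by at most 3 days.
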